Outcome at Day 7	Participants with Influenza A; Assumed Percentages in Each Category	
	IVIG (N=116)	Placebo (N=116)
Death	1.0	1.8
ICU (for FLU 003, assumed those ventilated were in the ICU)	1.9	3.6
Non-ICU hospitalization, O ₂	9.1	15.6
Non-ICU hospitalization, no O ₂	9.7	14.1
Discharged, not back to normal activities	37.8	39.0
Discharged, back to normal activities	40.5	25.8

D. Analysis Set

The analysis set for the primary efficacy and safety analyses and all other analyses will exclude 21 randomized participants:

- 4 participants who declined to receive an IVIG/placebo infusion; and
- 17 participants at a single site in Thailand for whom eligibility based on the NEW score could not be confirmed and data alteration of the vital signs used to compute the NEW score was suspected.

One other participant (at a different site) did not meet strict eligibility criteria. This participant had a locally determined positive influenza test 4 days prior to randomization instead of within 2 days as stated in the protocol. This participant will be retained in the

primary analysis because this was not considered to be major, there was no evidence that it was intentional, and it is in keeping with the intention to treat principle. Thus, analyses in the final report will be restricted to 308 randomized participants. These analyses will be referred to as modified intention to treat.

For the primary efficacy analysis, missing day 7 outcomes (4 participants have missing outcomes among those infused) will be imputed for participants who were infused.

Sensitivity analyses will be carried out to assess the impact of including participants from the pilot study, to assess the impact of imputation for the primary outcome, and to assess the impact of the exclusion of participants from the site in Thailand.

The four sensitivity analyses are:

- 1) An analysis that excludes participants enrolled in the IVIG pilot (16 participants).
- 2) An analysis that excludes participants for whom the day 7 outcome is missing (4 participants).
- 3) An analysis that includes the 17 participants who may not have met the NEW score eligibility criteria at the site in Thailand.
- 4) An analysis that excludes all participants at the site in Thailand (80 total) for which the eligibility of 17 participants could not be confirmed.

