If a NEW score is not available on Day 3, the last available follow-up NEW score will be used.

For the favorable outcome on Day 7, for the 4 participants who are missing the primary outcome on Day 7, it is presumed that they did not die or were re-hospitalized following discharge, i.e., they will be considered as having a favorable outcome.

H. Supportive Efficacy Endpoints

The following efficacy outcomes are defined as supportive:

- Time to discharge
- Time to death
- Percentage alive and out of the hospital at day 28
- Change in nasopharyngeal viral load from baseline to day 3
- Change in HAI titers from baseline to day 1, 3 and 7
- Percentage dying or requiring re-hospitalization after discharge
- Percentage with a diagnosis on or after the day of randomization and before the day 28 visit developing acute respiratory distress syndrome, acute renal failure, sepsis, pneumonia, enteritis or bronchitis (considered individually and also any of the diagnoses)
- Ordinal outcome on day 14
- Percentage alive and out of the hospital at day 14
- Resumption of normal activities at day 14.
- Ordinal outcome on day 28

Analysis Considerations for Supportive Efficacy Outcomes

Kaplan-Meier curves will be used to summarize the time to discharge and time to death, overall and through 7 days. The median number of days from randomization to discharge will be estimated. Deaths during hospitalization will be censored after day 28 (or day 7) for analyses of time to discharge. A logrank test will be used to compare treatment groups.

For participants who experienced multiple hospitalizations during follow-up, the time to the last discharge before day 28 will be considered. As the visit window for the day 28 visit extends to day 35, events after day 28 but prior to the final visit will be included in these analyses.

The difference between the IVIG and placebo group for change in log-transformed nasopharyngeal viral load from baseline to day 3 will be summarized using stratified analysis of variance with baseline viral load as a covariate. Viral loads vary by subtype. Therefore, strata will be defined by influenza virus subtype (H1N1, H3N2, or B) as well as geographic region. In these analyses, levels below 75 copies, the lower limit of detection, will be imputed as 75 copies. For this analysis, deaths (currently one

participant) on or before day 3 will be excluded, as will participants with undetectable RNA.

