The IVIG and placebo group will also be compared for the percentage with undetectable viral RNA at day 3 using logistic regression with baseline viral load as a covariate and geographic region and influenza subtype as stratifying factors. For this analysis, exclusions will be as per the previous paragraph; however, participants dying on or before day 3 (currently one participant) will be included in these analyses and considered as having detectable RNA.

Ordinal outcomes will be summarized using a proportional odds model as described for the primary ordinal outcome (see E.).

Binary outcomes will be summarized with logistic models that are stratified by geographic region and include indicators for the participant's clinical status at entry (ICU, general ward on supplemental oxygen, general ward not on supplemental oxygen), and an indicator for whether the participant was in the IVIG pilot trial (FLU 005) or the FLU-IVIG trial (FLU 006).

Reference viruses used for HAI titers changed over the course of the study corresponding to the circulating viruses. Longitudinal random effects models stratified by subtype (H1N1, H3N2, B) will be used to estimate differences in log-transformed HAI titers between the IVIG and placebo group at days 1, 3 and 7. Baseline HAI levels will be included in these models as a covariate. Each HAI titer assessed will be used to compare the two treatment groups. In addition, analyses specific to the virus of infection, will be carried out. For participants infected with H1N1, A/California/2009 and A/Michigan/2015 will be used; for those infected with H3N2, A/Hong Kong/2014, A/Switzerland/2013 and A/Texas/50/2012 will be used; and for those infected with influenza B virus, B/Phuket/2013, B/Brisbane/2008 and B/Massachusetts/2012 will be used.

I. Safety Endpoints

Targeted symptoms are collected at baseline day 3 and day 7. Unsolicited grade 3 or 4 adverse events are collected on days 1-3, 7, 14, and 28. SAEs are collected throughout the 28 day follow-up. The following will be summarized:

- Percentage of participants for whom infusion was interrupted.
- Percentage of participants with adverse events of grade 3 or 4 severity.
- Percentage of participants with a serious adverse event (SAE).
- Percentage with a composite outcome of death, SAE, infusion interruption, or any grade 3 or 4 adverse event.
- Percentage of participants with each targeted symptom on day 3 and on day 7

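### Setting Day 3 viral loads below 75 copies to 75 in a linear model biases the estimated IVIG effect toward zero by roughly the share below the limit, a share the documents do not give

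*SAP*

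**What the plan says.** SAP section H lists change in nasopharyngeal viral load to Day 3 among eleven outcomes under the statement "The following efficacy outcomes are defined as supportive". No power or detectable difference is given for it.

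The two arms are compared on the log scale by a linear model: their difference "will be summarized using stratified analysis of variance with baseline viral load as a covariate". Strata are influenza subtype and geographic region. For low values, "In these analyses, levels below 75 copies, the lower limit of detection, will be imputed as 75 copies". Deaths "on or before day 3 will be excluded, as will participants with undetectable RNA". Neither the substitution rule nor the exclusion of undetectable RNA names a visit.

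The next paragraph adds a binary comparison: "The IVIG and placebo group will also be compared for the percentage with undetectable viral RNA at day 3 using logistic regression", with the same covariate and strata. It carries the exclusions over ("For this analysis, exclusions will be as per the previous paragraph"), except that early deaths are kept and counted as detectable.

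No censored-data model is named. None of the four sensitivity analyses in SAP section D concerns the substitution; they cover the pilot participants, missing Day 7 outcomes and one site.

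**The concern.** A result below the limit of detection says only that the load is under 75 copies. Recording it as 75 assigns the highest value it could have. If IVIG lowers viral load, more IVIG than placebo participants fall below the limit, so the fall is understated more often in the IVIG arm and the estimated difference moves toward zero.

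Day 3 is the only post-baseline swab (protocol section 3.9.4 and Appendix B), so this is the trial's only effect estimate on the viral load scale. Protocol objective 3.3.2e relates viral load change to clinical outcome. A shrunken estimate could be read as weaker antiviral activity than was present. The SAP notes that viral loads differ by subtype. If the share below the limit also differs, the shrinkage could differ between influenza A and B.

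**Working it through.** **Which visit the exclusion means.** The logistic analysis compares the percentage undetectable at Day 3 under the same exclusions. If Day 3 undetectables were excluded, everyone left would be detectable and there would be nothing to compare. The substitution rule would also have almost no Day 3 values to act on. Reading the exclusion as undetectable at baseline makes both rules workable: Day 3 values below 75 then stay in and are set to 75. This is an inference, since the SAP does not say it.

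**Inputs.** From the documents: limit 75 copies, so c = log10(75) = 1.875; linear model with baseline covariate; 1:1 allocation; at most 308 participants ("analyses in the final report will be restricted to 308 randomized participants"). Not in the documents, and therefore assumed: share below 75 at Day 3 (5% to 60%), SD of log10 load (1.0 to 2.0), true shift (0.3 to 1.0 log10), and two-sided alpha 0.05 for this endpoint. The plan has no figure of its own to reproduce here.

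**Formula.** For normal Y with mean m and SD s, and a = (c − m)/s, the mean after substitution is

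E[max(Y, c)] = c·Φ(a) + m·(1 − Φ(a)) + s·φ(a).

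Its derivative in m is P(Y > c). A small constant shift is therefore multiplied by 1 minus the share below the limit. This holds for any location-shift distribution, not only the normal.

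**Worked case: s = 1.5, true shift 0.50, pooled share below 75 = 20%.**

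- Placebo: m = 3.405, share below 15.4%, mean after substitution = 1.875 × 0.154 + 3.405 × 0.846 + 1.5 × 0.237 = 3.525.
- IVIG: m = 2.905, share below 24.6%, mean after substitution = 1.875 × 0.246 + 2.905 × 0.754 + 1.5 × 0.315 = 3.124.
- Estimated difference 0.401 against a true 0.50, so 80% is kept.

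**Range over SD 1.0 to 2.0 and shift 0.3 to 1.0 log10.**

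| Pooled share below 75 | Fraction of true effect kept |
|---|---|
| 5% | 0.95 to 0.96 |
| 10% | 0.90 to 0.92 |
| 20% | 0.80 to 0.82 |
| 30% | 0.70 to 0.72 |
| 40% | 0.60 to 0.61 |
| 50% | 0.50 |
| 60% | 0.39 to 0.40 |

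**Simulation with a baseline covariate** (308 participants, SD 1.5, baseline correlation 0.5, 800 replicates, true shift 0.50):

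| Share below 75 | Substitution keeps | Tobit keeps | Power, substitution | Power, Tobit |
|---|---|---|---|---|
| 10% | 0.900 | 0.998 | 0.925 | 0.925 |
| 20% | 0.799 | 0.996 | 0.881 | 0.891 |
| 30% | 0.702 | 1.003 | 0.868 | 0.900 |
| 40% | 0.599 | 1.001 | 0.845 | 0.872 |
| 50% | 0.503 | 1.004 | 0.792 | 0.839 |

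With uncensored data, power was about 0.92. With no true effect, substitution gave no bias and rejected in 4% to 6% of replicates.

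**The case against.** The strongest reply is that the SAP already analyses the Day 3 undetectable share by logistic regression, which needs no substituted value and corresponds to the protocol endpoint of percent shedding at Day 3. If IVIG moves more participants below 75 copies, that comparison shows it. This stands, and it limits the risk of misreading. It does not replace the estimate, because an odds ratio for detectability gives no log10 effect size.

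A second reply is that the simulation favours Tobit: data were generated as normal with a constant shift continuing below the limit, which is Tobit's own model. This also stands. If some participants have cleared the virus, there is no normal lower tail, and the Tobit estimate rests on extrapolation that cannot be checked. It is a reason to show both estimates.

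A third reply is that the share may be small. The only viral load figures in the documents are the subgroup cut points of 100,000 (A) and 1,000,000 (B). If those lie near the centre of the distribution, loads start well above 75. With SD 1.5, a Day 3 mean of 4.0 log10 puts Φ((1.875 − 4.0)/1.5) = 8% below the limit, and a mean of 3.0 puts 23% below. These means are assumptions, but they show that a small share is plausible.

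Finally, the link to objective 3.3.2e is weaker in the SAP. Section N makes the explanatory analysis exploratory and conditional on a Day 7 difference, and it does not name viral load.

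**Conclusion.** The point holds on the baseline reading of the exclusion. Substituting 75 and fitting a linear model pulls the estimated log10 difference toward zero, to about 1 minus the pooled share below 75 copies. That rests on a constant log-scale shift continuing below the limit, which cannot be observed.

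A reader might infer more than the documents support:

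- That the effect in this trial will be understated by a third or a half. The Day 3 share is not given, so the loss could be about 5% or about 50%.
- That the test is invalid. The bias is toward no effect and type I error is not inflated. Power loss against Tobit was about 0.01 at a 20% share and 0.05 at 50%.
- That every Day 3 value below 75 is certainly substituted. The exclusion sentence leaves the visit open. Were Day 3 undetectables excluded instead, the problem would be a different one, selection on a post-randomization outcome: the fraction kept in the same simulation was 0.77 at a 10% share and 0.43 at 50%. The companion analysis argues against that reading.
- That the trial's main conclusions are at risk. The endpoint is supportive, and no primary or key secondary result depends on this rule.

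This is a cheap improvement to the trial's one quantitative virologic estimate.

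**What to change.** In SAP section H:

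1. State that the exclusion for undetectable RNA refers to baseline, if that is what is intended.
2. Report the number and percentage below 75 copies at Day 3 by arm, so that readers can judge the shrinkage.
3. Estimate the Day 3 difference by left-censored normal (Tobit) regression of log10 viral load, censored at log10(75), with the same baseline covariate and the same subtype and region strata. Report it with its 95% CI alongside the 75-copy substitution analysis.

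The cost is a few sentences of SAP text and one standard procedure, with no new data. The downside is that Tobit assumes normal log loads and a constant shift below the limit. Neither can be checked, so both estimates should be shown.

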3.8.1 Inclusion Criteria

INSIGHT 006: FLU-IVIG

- 1. Signed informed consent
- 2. Age ≥ 18 years of age
- 3. Locally determined positive influenza test (by PCR or other nucleic acid test, or by rapid Ag) from a specimen obtained within 2 days prior to randomization
- 4. Onset of illness no more than 7 days before randomization, defined as when the patient first experienced at least one respiratory symptom or fever
- 5. Hospitalized (or in observation unit) with influenza, with anticipated hospitalization for more than 24 hours.
- 6. For women of child-bearing potential: willingness to abstain from sexual intercourse or use at least 1 form of hormonal or barrier contraception through Day 28 of the study
- 7. Willingness to have blood and respiratory samples obtained and stored
- 8. NEW score ≥ 2 at screening (see Table 3)

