3.9.1 Screening and Baseline

Consenting participants will have the following screening/baseline information and measurements collected.

Within 2 days prior to randomization

- Demographics and medical history
- For women of child-bearing potential, a pregnancy test
- Assessment of NEW score
- Use of antiviral treatment
- · Laboratory confirmation of influenza
- Clinical data
- Local labs:
 - o CBC with differential white cell count, hemoglobin, hematocrit, platelets
 - Blood chemistries: sodium, potassium, serum bicarbonate, BUN, creatinine, glucose, albumin, ALT/GPT, AST/GOT, total bilirubin, PTT, PT, INR

On the day of randomization (Day 0)

Targeted symptoms

INSIGHT 006: FLU-IVIG

- Assessment of NEW score (if not already performed for screening on Day 0)
- Serum specimen for central lab (sufficient for 4 1-mL transport tubes, for serology testing and stored sample)
- Plasma specimen for central lab (sufficient for 4 1-mL transport tubes, for stored sample)
- Nasopharyngeal (NP) swab for quantitative PCR (1 swab in 3mL VTM)

Screening and baseline data and specimen collection requirements are summarized in tabular form in Appendix B: *FLU-IVIG Time and Events Schedule*. Details of specimen handling can be found in the *INSIGHT FLU-IVIG Laboratory Manual*.

For participants who consent to the separate INSIGHT Genomics study (INSIGHT 004), a whole blood sample will be obtained for DNA extraction to study polymorphisms in immune response genes and other genetic variants that may be associated with an increased risk of respiratory diseases due to influenza.

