To supplement the overall summary odds ratio, separate odds ratios will be estimated for each dichotomized definition of improvement that can be formulated from the components of the ordinal outcome. A test for the proportionality assumption will also be made.

Analyses identical to those described above (including the imputation) will be carried out for participants with influenza A virus infection. If the central determination of influenza resulted in negative or indeterminate results, the local determination will be used. For participants with a co-infection with A and B influenza subtypes, the participant will be classified as A.

The analyses described above will be carried out for the primary efficacy analysis and for the two planned sensitivity analyses.

These analyses will be supplemented with summaries which give the category percentages for the primary ordinal outcome by treatment group for days 1-7.

F. Subgroup Analysis

Analyses will be carried out for the following baseline-defined subgroups:

- Influenza strain (A, B) and subtype (pH1N1, H3N2, B)
- Age (<40, 40-59, ≥ 60 years)
- Gender (men, women)
- Race/ethnicity (White/Hispanic/other, Black, Asian)
- Enrollment ward/use of O₂ (ICU, general ward on O₂, general ward not on O₂)
- Geographic region (United States/South America/Mexico, Europe/Australia, Thailand)
- Northern/Southern hemisphere/Equatorial (United States, Mexico, and Europe vs Australia and South America vs Thailand)
- Duration of symptoms prior to randomization (≤ 3, 4, ≥ 5 days)
- New score (≤ 3, 4-5, ≥ 6)
- Influenza season (Oct2013-Sep2014, Oct2014-Sep2015, Oct2015-Sep2016, Oct2016-Sep2017, Oct2017-Jun2018)
- Co-morbidities (CVD, COPD/asthma, diabetes, none of these) (as hierarchy)
- Other conditions (sepsis, pneumonia, immune suppression) (each considered separately versus not having the condition)

- Influenza strain/viral load (A and viral load > 100,000/≤ 100,000, B and viral load > 1,000,000/≤ 1,000,000) (4 categories)
- Influenza vaccination (yes, no, unknown)
- Smoking status (current smoker, non-smoker)
- IVIG lot (1-5)
- HAI titer (highest titer measured)
- HAI titer corresponding to subtype of infection (highest titer measured)
- Risk score tertile for hospitalization or death at day 7

The following special situations will apply to the categorization of participants for subgroup analyses:

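### Does the exclusion for undetectable RNA, which names no swab day, undermine the day-3 viral load analyses?

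*SAP*

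**What the plan says.** SAP section H, under the analysis considerations for supportive outcomes, has two consecutive paragraphs on viral load.

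- **Change analysis.** The outcome is the change in log viral load between the Day 0 and Day 3 swabs, adjusted for baseline and stratified by subtype and region. A floor applies: "levels below 75 copies, the lower limit of detection, will be imputed as 75 copies". Deaths "on or before day 3 will be excluded, as will participants with undetectable RNA". No swab day is attached to the RNA condition.
- **Binary analysis.** The arms are compared on the "percentage with undetectable viral RNA at day 3 using logistic regression", adjusted for baseline load. Here "exclusions will be as per the previous paragraph", with one reversal: early deaths "will be included in these analyses and considered as having detectable RNA".

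Other provisions bear on the intent. Protocol 3.8.1 admits patients on a "Locally determined positive influenza test (by PCR or other nucleic acid test, or by rapid Ag"), so entry does not depend on the central laboratory. Protocol 3.9.1 takes a Day 0 "Nasopharyngeal (NP) swab for quantitative PCR". SAP section E expects some central results to fail: "If the central determination of influenza resulted in negative or indeterminate results, the local determination will be used". SAP section F repeats that provision for subgroup classification.

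**The concern.** The SAP calls 75 copies the lower limit of detection, so undetectable means below 75 copies. An exclusion covering day 3 would then have three consequences:

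1. Every day-3 value that the floor is meant to handle would already have been removed.
2. The binary model would lose every participant who can be an event. The only group restored, early deaths, is coded as a non-event. The model could not be fitted.
3. The analysis set would be selected on a post-randomization outcome that treatment is meant to change.

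The binary analysis corresponds to the day-3 shedding endpoint in Protocol 3.4, so a listed endpoint would be lost. The next paragraph of the SAP does name day 3 when it means day 3, which makes the omission here more noticeable.

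**Working it through.** The documents give no viral load distribution, event count or power for these analyses, so there is no stated figure to reproduce. The check has two parts.

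**1. Logic, with no assumptions.** Let B mean undetectable on the Day 0 swab and D undetectable on the Day 3 swab. The floor acts on B or D values; the binary event is D.

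| Reading of the exclusion | Who is dropped | Day-3 values left for the floor | Events left |
|---|---|---|---|
| Baseline | B | D without B | D without B |
| Both swabs | B and D together | D without B | D without B |
| Day 3 | D | none | none |
| Either swab | B or D | none | none |

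The first two readings give the same events. They differ only in whether participants undetectable at baseline but detectable at day 3 stay in. The last two give no events, by definition.

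**2. Illustrative counts.** Only N = 308 (SAP section D) and the limit of 75 copies (SAP section H) come from the documents. Assumed: baseline log10 load with mean 4.8 and SD 1.5; mean fall of 1.0 to 2.5 log10; a further fall of 0.3 on IVIG; residual SD 1.2; 2,000 simulated trials per row; no subtype or region strata.

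Number expected to be undetectable at baseline: log10(75) = 1.875, so 308 × Φ((1.875 − 4.8)/1.5) = 308 × Φ(−1.95) = 308 × 0.0256 ≈ 8. About 308 − 8 = 300 remain.

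| Mean fall (log10) | Baseline reading: n | Events | Estimated effect | Either-swab reading: n | Events | Estimated effect |
|---|---|---|---|---|---|---|
| 1.0 | 300 | 48 | −0.25 | 252 | 0 | −0.24 |
| 1.5 | 300 | 70 | −0.23 | 230 | 0 | −0.23 |
| 2.0 | 300 | 98 | −0.20 | 202 | 0 | −0.21 |
| 2.5 | 300 | 129 | −0.17 | 171 | 0 | −0.19 |

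In each row the lost participants are exactly the day-3 events: 300 − 252 = 48, 300 − 230 = 70, 300 − 202 = 98, 300 − 171 = 129. The both-swabs reading gave 300 or 301 participants, with the same events and the same effects as the baseline reading.

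**Which reading the text supports.** Set side by side, the provisions point one way. A floor at the detection limit is needed only if some undetectable values stay in; with baseline undetectables removed, the values left for it are the day-3 ones. A model for undetectable RNA at day 3 cannot be meant to exclude its own events. Entry on a local test, with central negatives foreseen, explains why a baseline exclusion is wanted: someone with no detectable virus at entry has no measurable fall to analyze.

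**The case for a change.** The best case for amending runs as follows. A prespecified plan should run as written, without the programmer having to infer a time point. The SAP was prepared by blinded statisticians, and settling an analysis set after unblinding invites challenge. The phrase also governs several results: two viral analyses, in two populations (all participants and influenza A, SAP section G), in three analysis sets (the main one and sensitivity analyses 3 and 4, SAP section D), so 2 × 2 × 3 = 12. The wrong reading could also cost power. With assumed inputs (n = 300, a true difference of 0.4 log10, baseline slope 0.6, 20% undetectable at day 3), power is 0.72 with the floor and 0.48 with exclusion.

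It stands that the time point is absent and that naming it would cost almost nothing. The rest carries less weight. The day-3 and either-swab readings produce a model with no events, which would be seen at once and could not pass into a reported result. Because the binary analysis borrows its exclusions from the change analysis, ruling those readings out for one rules them out for the other. That leaves the baseline and both-swabs readings, which were almost indistinguishable in the simulated scenarios. The power figures rest wholly on assumed inputs and describe a reading the authors probably did not intend, so they do not measure a flaw in the plan.

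**Conclusion.** No change follows. The exclusion lacks a time point, but its neighbors supply one: baseline, meaning the central Day 0 swab. On that reading the 75-copy floor, the day-3 endpoint and the handling of early deaths all work together. The damaging consequences arise only if the exclusion is extended to day 3, which the text does not say and which its own endpoint contradicts.

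The reach is small. The change in viral load is one of eleven listed supportive endpoints, and the day-3 undetectable percentage appears only in the accompanying analysis text. The primary and key secondary analyses do not use either.

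The zero-event result and the equal event sets under the baseline and both-swabs readings follow from definitions. The counts of about 300 participants and 48 to 129 events depend on assumed viral load distributions and serve only to show that a workable analysis remains. The conclusion rests on inferred intent, which neither document states outright. A part of SAP section E was not available to me; as that section covers the primary analysis, it is unlikely to define this exclusion.
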